4.2.2 Investigational centers

Several selected centers will participate in the study. The list of Investigators will be managed separately from the study protocol and Competent Authorities will be kept informed of the update of the list.

Patients will be recruited during hospitalization.

4.2.3 Identification of the subjects

During or at the end of the research, the data transmitted to the sponsor by the investigators (or any other specialized contributors) will be rendered non-identified. Under no circumstances should the names or addresses of the participants be made clear. The sponsor will ensure that each person who is subject to the research has given his or her consent for access to individual data concerning him or her that are strictly necessary for the research.

For this research, the subjects will be identified as follows:

Centre No. (3 numerical positions) - Selection order No. of the person in the centre (4 numerical positions) - surname initial - first name initial

This reference is unique and will be retained for the entire research period.

4.2.4 Randomisation

After screening for inclusion and non-inclusion criteria, and obtaining consent, patients will be randomized (1:1 ratio) to cilostazol or placebo groups by logging onto a randomization website using a pre-prepared randomization list, balanced by randomly variable block size. Randomization will be stratified by centre, age (<50 years; >=50 and <=75 Years; >75 years); and severity (Fisher grade from I to III; Fisher grade IV)

"CASH" protocol, version 2.1 of 04/04/2025

Randomisation will occur in an online data entry platform, guaranteeing the concealment of the experimental arm assigned to the doctor performing the inclusion and randomisation of the patient.

The randomisation code will be disclosed once recruitment is completed.

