4.2.5 Blinding methods and provisions put in place to maintain blindness

The physician investigator in each participating ICU will, after the patient fulfils the inclusion criteria and gives consent to participate in the CASH trial, use the online platform for data entry to randomize the patient, which in turn will allocate the participant to one of the two groups, from a pre-prepared randomization list.

The randomization will be held in an online platform for data entry, and as such, ensures allocation concealment by not releasing the randomization code until the recruitment is completed.

At the moment of randomisation in the e-CRF, visible to the investigator will only appear that "*the patient was successfully randomised*"; no other code will appear in the e-CRF. At the moment of randomisation, an email will inform the hospital pharmacy that a patient has been included and randomised; only the pharmacist will have access to the randomisation arm.

Both trial participants, care providers, and outcome assessors will be blinded after the patients' assignment to one of the trial groups. The double blinding will be provided by the hospital pharmacy of promotor establishment using placebo pills similar to commercial pills. Nurses in charge will be blind to the study as well as the physician and research technician in charge of outcome assessment.

In case of accidental loss of treatment, a form has to be completed with informations regarding the reason of the loss, the number of the patient and the number of days of treatment. The promotor will process the accident and will authorize or not the pursuit of the treatment. If the authorization is granted, the investigator site has to complete a form in the e-CRF for exceptional dispensing and will receive the code allowing the good dispensation according to the randomisation arm.

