5.3 End of research visit at 6 months

The end of research visit will be made at 6 months or when the patient terminates the study.

Primary outcome

The physician, physical therapist, research assistant or research nurse will collect blindly the mRS if the patient is alive. A face-to-face structured interview will be held during which the modified Rankin scale will be assessed (Appendix 1, 17).

Functional and cognitive status will be collected during the patient's consultation at 6 months, with using:

- SAHOT Score
- MOCA score
- Return to work
- Activities of Daily Living
- Instrumental Activities of Daily Living

The in-hospital morbidity indicators will be collected, including:

- Length of Intensive Care Unit stay
- Length of hospital stay

The occurrence of cerebral vasospasm and DCI during ICU stay will be assessed, with collecting

-Delayed cerebral ischemia, defined as the occurrence of focal neurological deficit or a decrease of at least 2 points on the Glasgow Coma Scale, which does not occur immediately after aneurysm occlusion and which is not ascribable to other causes.

[figure not shown]
-Cerebral artery vasospasm, defined as a reduction of the diameter of the proximal cerebral artery on either CT-, MR- or catheter angiography

-Cerebral infarcts, considered when detected on the CT scan or MRI performed with 6 weeks, (or on the latest CT scan or MRI performed before death within 6 weeks, or at autopsy), but not present on the earlier CT or MRI scan performed between 24 and 48 h after early aneurysm occlusion and not ascribable to other causes

5.4 Expected length of participation and description of the chronology and duration of the research.

Inclusion period	42 months
The included subjects' length of participation, of which:	

 • Treatment period: • Follow-up period: 	2 weeks 6 months
Total research period:	49 months

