8 ASSESSMENT OF EFFICACY

8.1 Description of parameters for assessing efficacy

Primary outcome

It is the Modified Rankin score (mRS):

It will be assessed at 6 months by physicians, physical therapists or research assistant or research nurses who would have been specifically trained to pass this score and who will be unaware of the trial-group assignments, during a face-to-face interview with patient. This structured interview will strengthen the interrater agreement (17)

Methods for secondary assessment criterion collection

At the 6 months interview and after collection of the mRS, one will proceed to the assessment of

- The SAHOT score (Appendix 2). For facilitating its collection and reduce time of the consultation, the SAHOT questionnaire will be sent to the patients before the 6 months face-to-face interview.
- MOCA score at 6 months (Appendix 3), which will be passed during the 6 months face-to-face interview by the trained investigator.
- Return to work at 6 months
- Activities of Daily Living (ADL) at 6 months (Appendix 4) and Instrumental Activities of Daily Living (IADL) at 6 months (Appendix 5), which will be passed during the 6 months face-to-face interview by the trained investigator.

Radiological endpoints will be collected daily during the ICU stay. Delayed cerebral ischemia is defined in the section 4.1.2 Highest velocity in the mean cerebral artery evaluated in tCD will be collected when available. MR/CTA DSA vasospasm will be scored as mild, moderate or severe according to the narrowing of the cerebral arteries.

8.2 Anticipated methods and timetable for measuring, collecting and analysing the parameters for assessing efficacy

Efficacy will be assessed with help of the mRS at 6 months, during a structured face-to-face interview of the patients which will involve one of the physicians, physical therapists, research assistants or research nurses of any participating centre. The organisation of the structured "CASH" protocol, version 2.1 of 04/04/2025

face-to-face interview will be as similar as possible between centres. During this M6 visit, the secondary outcomes- related scores will also be collected:

- SAHOT
- MOCA score
- Activities of Daily Living
- Instrumental Activities of Daily Living
- Return to work

During hospital stay, other parameters evaluating efficacy will be prospectively collected and reported on the e-CRF:

- Length of stay in the ICU
- Length of hospital stay
- 28-day mortality

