10.3.6.1 Analysis and declaration of serious adverse events

The sponsor assesses:

- the seriousness of all adverse events reported
- the causal relationship of these events with each experimental medication and/or specific medical procedures/exams added by the research and with other possible treatments
- the expected or unexpected nature of these adverse reactions

All serious adverse events which the investigator and/or the sponsor believe could reasonably have a causal relationship with the experimental medication are considered as suspected adverse reactions.

All suspected unexpected serious adverse reactions (SUSAR) are declared by the sponsor, within the legal time frame, to the Agence Française de Sécurité Sanitaire des Produits de Santé (ANSM, French Health Products Safety Agency) and to the relevant Comité de Protection des Personnes (CPP, ethical committee).

- The initial declaration must be made with no delay after the date on which the serious adverse event occurs in the case of death or of a life-threatening diagnosis.
- The initial declaration must be made with no delay after the date on which the serious adverse event occurs in the case of other serious situations.
- The follow-up declaration must be made with no delay.

Any suspected unexpected serious adverse reaction must also be declared electronically in the Eudravigilance European database for adverse events due to medications, established by the European Medicines Agency (EMA).

The sponsor must notify all relevant investigators about any data that could adversely affect the safety of the research subjects.

Specific cases of serious adverse events of special interest:

At the request of ANSM, the sponsor may be asked to declare serious adverse events of special interest, in accordance with the same procedures and deadlines as SUSARs.

Specific case of double-blind trials

As a general rule, the sponsor declares a suspected unexpected serious adverse reaction to the competent authorities and to the CPP after having broken the blind on the experimental medication.

In exceptional situations, and if the ANSM grants permission when requested by the sponsor in the sponsor's clinical trial authorisation application, the methods for unblinding and for declaring suspected unexpected serious adverse reactions can be modified. These methods will then be defined in detail in the research protocol (see section 4.2.6).

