Stage	Information proportion	Beta spent this stage	Cumulative beta spent	Percentage beta spent at this stage	Cumulative percentage
1	0.33	0.0264	0.0264	13.2	13.2
2	0.67	0.0901	0.1165	45.7	58.3
3	1.00	0.0835	0.2000	41.7	100.0

Boundary Probabilities for $\delta = -0.11$

Number of Simulations: 100000

Futility Boundaries: Binding

After Efficacy Boundary Crossing: Hold Out

After Binding Futility Boundary Crossing: Hold Out

 Alternative Hypothesis: $P1 - P2 < 0$ (one-sided)

P1: 0.65

P2: 0.76

 δ : -0.11

Stage	N1	N2	Efficacy		Futility	
			Boundary	Probability	Boundary	Probability
1	95	95	-3.7103	0.0253	0.2701	0.0277
2	189	189	-2.5111	0.4166	-1.1224	0.0885
3	284	284	-1.9308	0.3597	-1.9308	0.0821

Average N1: 226.

Average N2: 226

[figure not shown]

Figure 1.

12.6 Specify if subjects who leave the research prematurely will be replaced and in what proportion.

The primary outcome is assessed only one time 6 months after Day 0 (5 months and a half after last day of treatment) that could lead to patient's loss to follow up. Nevertheless, SAH is a serious condition that requires a long and close patient's monitoring. That will limit patient's loss to follow up. The patients who leave study prematurely (for loss to follow up or death) won't be replaced and will be considered as non responder patients in the main analysis of primary criterion.

Some sensitivity analyses will be performed with complete cases only.

Only, the particular circumstance of patient resignation will lead to exit patient of the primary analysis. A 10% rate of non evaluable patients is foreseen.

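### The randomisation code is to be released at the end of recruitment, when about 90 of 630 blinded 6-month mRS assessments (14%) are still to come

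*Protocol*

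**What the plan says.** Two places in the protocol fix when the code is released:

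- Section 4.2.4: "The randomisation code will be disclosed once recruitment is completed". No recipient is named and no condition is attached.
- Section 4.2.5: the online platform "ensures allocation concealment by not releasing the randomization code until the recruitment is completed".

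Three places commit to a blind that has to last until the 6-month visit:

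- Section 4.2.5: "Both trial participants, care providers, and outcome assessors will be blinded".
- Section 5.3, on the 6-month visit: the assessor "will collect blindly the mRS if the patient is alive".
- Section 8.1: the mRS is scored by trained staff "who will be unaware of the trial-group assignments".

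On timing, section 12.6 says "The primary outcome is assessed only one time 6 months after Day 0". Section 5.4 gives 42 months of inclusion, 6 months of follow-up and 49 months in total. Section 5.6 places the end of the trial at the last visit of the last patient.

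**The concern.** Allocation concealment and blinding end at different times. Concealment protects the decision to enrol, so it has done its work when the last patient is randomised. Blinding of the outcome has to last until the last mRS is scored. The protocol gives only one release date, and it is the one that suits concealment.

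The mRS is scored by a rater at interview and split at 2 for the primary analysis. If the arm were known, it could influence the rater, the patient's answers and the effort made to bring patients back for the visit. That effort matters because, under section 12.1, a missing 6-month value is replaced by the mRS at ICU discharge, or counted as non-response if there is none. The 6-month secondary outcomes, including the patient-completed SAHOT, are exposed in the same way.

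Two other steps can also fall after release. The adjudication committee, which must work blind, meets when all patients have been monitored (section 9.3). The SAP has to be final only before database lock (section 12.1).

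**Working it through.** **The denominator.** Section 12.5 gives 284 patients per arm, 630 in total after allowing for 10% dropout.

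- A simulation of the three-look design (95, 189 and 284 per arm; favourable outcome 65% against 76%; the z boundaries tabulated in 12.5; 400,000 runs) gives power 0.800, against the stated 0.8016, and one-sided type I error 0.025.
- 2 × 284 = 568, and 568/0.90 = 631.1, or 632 with equal arms, against the stated 630. The figure of 630 is sound for this purpose.

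**The calendar.** Inclusion ends at month 42, so the code is released then. The last 6-month mRS falls at 42 + 6 = month 48, within the stated 49.

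**Primary outcomes pending at release.** Uniform accrual is assumed, because the protocol gives no accrual curve.

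- Accrual: 630/42 = 15 patients per month.
- Pending: 15 × 6 = 90, and 90/630 = 14.3%.

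**Range for accrual in the last six months.**

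| Late accrual relative to average | Per month | Pending | Share of 630 |
|---|---|---|---|
| 0.5 | 7.5 | 45 | 7.1% |
| 1.0 | 15 | 90 | 14.3% |
| 1.5 | 22.5 | 135 | 21.4% |

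As a cross-check, the protocol's 1.9 patients per centre per month gives 8 × 1.9 × 6 = 91 (14.5%) with 8 centres and 9 × 1.9 × 6 = 103 (16.3%) with the stated 9. The per-centre figures in section 6.3 (79 and 1.9) fit 8 centres (630/8 = 78.75; 78.75/42 = 1.875) and not 9 (70 and 1.67). That is a separate inconsistency and does not enter the calculation above.

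**From pending outcomes to rated interviews.** Not all 90 lead to an interview.

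- With the protocol's 10% dropout: 90 × 0.90 = 81 evaluable.
- Patients who have died score 6 without any judgement. If the roughly 30% mortality quoted in section 10.3.3.1 applied in full, and all of those deaths had already occurred: 90 × 0.70 = 63 (10.0% of 630). Section 12.5 says early deaths are not included, so the trial's own mortality may be lower.

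**Patients still in the 14-day treatment period at release.** 15 × 14/30.44 = 6.9, about 7 (3.4 to 10.3 over the same accrual range). This is an upper figure, because section 5.8.1.1 stops treatment when the patient leaves the ICU.

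**With the code held until the last mRS and database lock.** Pending outcomes at release: 0 of 630.

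**The case against.** The best defence is that the protocol never says the code goes to raters, patients or carers. Release to the sponsor or the analyst alone would be compatible with every blinding commitment. Section 4.2.5 limits access to the arm to the pharmacist, and the commitments in 4.2.5, 5.3 and 8.1 carry no end date. Section 4.2.5 also links the date expressly to concealment, and withholding the code until a date does not require release on that date. On this reading the text is loosely worded concealment language, and the specific rules on assessors prevail. Further, 90 counts pending outcomes and not exposed interviews.

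Part of this stands. No recipient is named, so unblinding of any particular assessment is not shown. The figure of 90 is an upper one for rated interviews under uniform accrual.

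The rest does not remove the problem. The sentence in 4.2.4 is a positive and unqualified statement that the code will be disclosed. The pharmacist's exclusive access is described for the moment of randomisation and does not limit a later disclosure. The protocol has two later milestones to hand, the last visit and database lock, and ties release to neither. Section 7.3 leaves the correspondence of patient and kit codes to a Pharmacy Manual that is not shown; it cannot be assumed to override a date fixed in the protocol.

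**Conclusion.** The concern holds. Sections 4.2.4 and 4.2.5 set a release date that conflicts with the protocol's own commitment to a blinded 6-month mRS. If that date is followed, nothing written protects the blind for the last cohort. Under uniform accrual this cohort is about 90 of 630 primary outcomes (14%), with a range of 45 to 135 (7% to 21%). After dropout about 81 would be evaluable, and under the most severe reading of mortality about 63 would still need a rater. The finding concerns the written rule and does not show that any rater will in fact be told the arm. It should be corrected before recruitment ends, because a blind once broken cannot be restored.

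**What to change.** In sections 4.2.4 and 4.2.5, replace the end of recruitment as the release date by the point at which the last 6-month mRS has been recorded and the database is locked.

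Add a cross-reference stating that existing provisions are unchanged: the dispensing pharmacist and exceptional dispensing (4.2.5), individual unblinding (4.2.6), and declaration of unexpected serious reactions "after having broken the blind on the experimental medication" (10.3.6.1). The interim arrangements in 12.7 also stay as they are. That section describes the interim analyses as blinded, so the cross-reference should not be worded as granting the monitoring committee access to the code.

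The cost is one sentence in 4.2.4, one clause in 4.2.5 and the cross-reference. No new visit, role or procedure is needed.

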4.2.5 Blinding methods and provisions put in place to maintain blindness

The physician investigator in each participating ICU will, after the patient fulfils the inclusion criteria and gives consent to participate in the CASH trial, use the online platform for data entry to randomize the patient, which in turn will allocate the participant to one of the two groups, from a pre-prepared randomization list.

The randomization will be held in an online platform for data entry, and as such, ensures allocation concealment by not releasing the randomization code until the recruitment is completed.

At the moment of randomisation in the e-CRF, visible to the investigator will only appear that "*the patient was successfully randomised*"; no other code will appear in the e-CRF. At the moment of randomisation, an email will inform the hospital pharmacy that a patient has been included and randomised; only the pharmacist will have access to the randomisation arm.

Both trial participants, care providers, and outcome assessors will be blinded after the patients' assignment to one of the trial groups. The double blinding will be provided by the hospital pharmacy of promotor establishment using placebo pills similar to commercial pills. Nurses in charge will be blind to the study as well as the physician and research technician in charge of outcome assessment.

In case of accidental loss of treatment, a form has to be completed with informations regarding the reason of the loss, the number of the patient and the number of days of treatment. The promotor will process the accident and will authorize or not the pursuit of the treatment. If the authorization is granted, the investigator site has to complete a form in the e-CRF for exceptional dispensing and will receive the code allowing the good dispensation according to the randomisation arm.

4.2.6 Procedures for breaking the blind, if applicable

Unblinding may be requested at any time and for any reason considered indispensable by the investigating physician, if a serious adverse event occur attributable to cilostazol, by calling the Délégation à la Recherche Clinique et à l'Innovation (Delegation for Clinical Research and Innovation) or the Pharmacy of Centre Hospitalier Sainte-Anne at the numbers given to each centre in the study protocol.

In exceptional cases in which curative anticoagulation or antiaggregation is deemed necessary by the caring physicians, unblinding will be realized and a 10-hour wash out period will be advised in case of belonging to the cilostazol arm.

5 PROCEDURE FOR THE RESEARCH

Consent will be obtained by an investigator from the patient, or from a relative if the patient is unable to consent, or using the emergency clause according to French Law if no relative could be contacted within 24 hours. If the patient is unable to consent, a pursuit consent will be sought as soon as the patient will be able to express its wills.

Visits will be conducted daily throughout the stay in intensive care until D28. If the patient has been discharged from the ICU, a visit will be made at D28 to collect primary and secondary outcome data. An electronic case report file will be available to the research team

of each institution, on an online platform (Research Electronic Data Capture, REDCap, Vanderbilt University, Study data will be collected and managed using REDCap electronic data capture tools hosted at Centre Hospitalier Sainte-Anne. REDCap is a secure, web-based software platform designed to support data capture for research studies, providing 1) an intuitive interface for validated data capture; 2) audit trails for tracking data manipulation and export procedures; 3) automated export procedures for seamless data downloads to common statistical packages; 4) procedures for data integration and interoperability with external sources.

5.1 Inclusion visit

Inclusion visit will be conducted by the investigator of the participating centres. The inclusion visit will allow to check the inclusion and non-inclusion criteria.

Inclusion criteria will be:

- Age >18 yo
- Admission to an ICU
- Aneurysmal SAH diagnosis made upon radiologic findings in CT scan or MRI
- Clinical onset of SAH within the last 96 hours -
- Aneurysm successfully secured by surgical clipping or endovascular coiling
- Consent of the patient or, if not possible, from a proxy (emergency clause)
- Registration in a national health care system

Non-inclusion will be

- Precritical modified Rankin Scale (mRS) > 2
- Non-aneurysmal SAH
- Delayed>96h admission after first symptoms of Aneurysmal SAH
- Coma defined by GCS of 3-5 with untreatable aneurysm will be excluded
- Known allergy to cilostazol
- Pregnancy
- Pre-existing major hepatic, renal, pulmonary or cardiac disease
- Concomitant use of one other anti-platelet and/or anticoagulant agent
- SAH diagnosed on LP with no evidence of blood on CT.
- Tutelage or guardianship

During the inclusion visit, the following characteristics will be collected:

Demographic data:

- Age
- Sex
- Medical history (High blood pressure, tobacco use, drugs use, cocaine use, n° Unit of alcohol/d consumed, diabetes and other comorbidities according to the Charlson score (see Appendix 6)

SAH history

- Date of onset
- Initial loss of consciousness
- Onset seizure
- Meningeal syndrome
- Sudden headache

Severity at hospital admission

- WFNS score
- GCS
- Motor deficit
- Pupillary status

Radiologic findings on first CT:

- Localisation of aneurism having bled (anterior, posterior circulation)
- Multiple aneurism
- Largest aneurism size (mm)
- Hjdra score,
- Fisher score
- Intraventricular haemorrhage
- Intraparenchymal hematoma
- Acute hydrocephalus
- Area of previous ischemia
- Area of recent ischemia
- Fisher scale (Appendix 9)

Specific complications up to inclusion:

- High intracranial pressure (ICP) when measured (normal ICP will be considered if not monitored) > 20mmHg
- **Radiological findings at inclusion or >6hours after aneurism treatment**
 - Area of recent ischemia
 - Recurrent bleeding
 - Acute hydrocephalus

Treatment up to inclusion:

- Time from symptoms to treatment (hours)
- Endovascular therapy
- Surgical clipping
- Hemicraniectomy
- Hematoma resection
- Lobectomy
- Mechanical ventilation
- Catecholamine administration
- Continuous sedation
- Extraventricular drainage
- Therapy intensity level (Annexe 5)

Clinical examination at the time of inclusion:

- SAH severity according to WFNS,
- GCS score,
- Neurological focal sign at admission
- Anisocoria

